4.4 Efficacy Variables/Endpoints

4.4.1 Primary endpoint

AKI_(48 hours) is defined as 50% increase in corrected creatinine within 48 hours. AKI_(48 hours) is calculated using screening creatinine (uncorrected) compared to 24 and 48 hours corrected creatinine.

Corrected creatinine [(creatinine (μmol/ml)/1000 x [1 + (fluid balance (L)_(+24 hours) / (weight (kg x 0.6)))] only calculated for day 1-3. For example for day 1 the Fluid balance measured at day 2 will be used. If negative values in fluid balances, fluid balance is set to 0.

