4.4.3 Secondary endpoints Follow up postop days 1-4

Fluid balance

- Fluid balance ((ml)
- Urine (ml)
- Weight (g)
- %FO (fluid balance (ml)/1000_(+24 hours) /preop weight (kg)) x 100. For example for day 1 the Fluid balance measured at day 2 will be used. If a negative fluid balance set %FO to 0.
- Cumulative %FO (day 1+2, day 1+2+3, day 1+2+3+4)

STATISTISKA KONSULTGRUPPEN		Statistical Analysis Plan	
Protocol: The prophylactic effect of Levosimendan in reducing acute kidney injury postoperatively in pediatric patients undergoing corrective heart surgery		Protocol No: MiLe-1	Version: 1.0 Page 12 of 17

- Peritoneal Dialysis day 1 and day 2 from Status and medication_1 and Status and medication_2

Morning lab results (Postop day 1 is under hemodynamics_1, etc.)

- Hb (g/L)
- Hct
- Leucocytes ($\times 10^9/L$)
- Trombocytes ($\times 10^9/L$)
- C R P (mg/L)
- Albumin (g/L)
- Creatinine ($\mu\text{mol}/L$)
- Corrected creatinine [$(\text{creatinine } (\mu\text{mol}/L) \times [1 + (\text{fluid balance } (L)_{(+24 \text{ hours})} / (\text{weight } (\text{kg}) \times 0.6)])]$ only calculated for day 1-3. For example for day 1 the Fluid balance measured at day 2 will be used. If negative values in fluid balances, fluid balance is set to 0.
- Corrected creatinine (age differentiated), same as above but (in the formula) using 0.75 for infants younger than 5 months and 0.6 for infants/adults older than 5 months.
- AKI_(72 hours) and AKI_(96 hours) in same fashion as in primary endpoint
- AKI stage at 48 (24 and 48), 72 and 96 hours.
 - Stage 0 (no AKI, corrected creatinine up to 1.49 times screening creatinine)
 - Stage 1 (corrected creatinine 1.5-1.99 times screening creatinine)
 - Stage 2 (corrected creatinine 2-2.99 times screening creatinine)
 - Stage 3 (corrected creatinine 3 (or more) times screening creatinine or need of dialysis)
- eGFR Creatinine (calculated value from CRF)
- Cystatin C (mg/L)
- eGFR Cystatin C, calculated using formula $91 \times \text{Cystatin C } (\text{mg/L})^{-1.213}$
- Urea (mmol/L) Use value in database (no recalculation is needed), in CRF the unit stands as $\mu\text{mol}/L$ but it is actually mmol/L.
- Combined eGFR (mL/min per 1,73 m²)
 - $39.1 \times [\text{height } (\text{m})/\text{Serum creatinine } (\text{mg/dl})]^{0.516} \times [1.8/\text{Cystatin C } (\text{mg/L})]^{0.294} \times [30/\text{Urea } (\text{mg/dl})]^{0.169} \times [1.099]^{\text{male}} \times [\text{height } (\text{m})/1.4]^{0.188}$

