5.5 Efficacy Analyses

5.5.1 Primary Efficacy Analysis

Logistic regression of AKI (50% increase in corrected creatinine within 48 hours) with treatment group independent variable will be used for the primary outcome. If differences in corrected creatinine at baseline differs between groups adjustment for baseline corrected creatinine will be made by adding baseline creatinine as an independent variable. The analysis will be two sided and with alpha 0.05.

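### The SAP's primary-endpoint formula for corrected creatinine carries a stray division by 1000 that its secondary-endpoint section does not have; a visible drafting error, to be corrected in 4.4.1

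*SAP*

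**What the plan says.** SAP 4.4.1 defines AKI within 48 hours as a 50% increase in corrected creatinine. The corrected value is creatinine, labelled µmol/ml, divided by "1000 x [1 + (fluid balance (L)_(+24 hours) / (weight (kg x 0.6)))] only calculated for day 1-3". The comparator is stated separately: "AKI_(48 hours) is calculated using screening creatinine (uncorrected) compared to 24 and 48 hours corrected creatinine". SAP 4.1.3 lists preoperative creatinine in µmol/L.

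SAP 4.4.3 lists a variable of the same name with the same fluid factor, the same use of the next day's fluid balance, the same rule for negative balances and the same limit to days 1-3. There creatinine is in µmol/L and nothing is divided by 1000. The recorded fluid balance is listed in ml, while both formulas use litres.

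Section 4.4.3 also stages AKI, covering the primary window: "AKI stage at 48 (24 and 48), 72 and 96 hours". The lowest categories are "Stage 0 (no AKI, corrected creatinine up to 1.49 times screening creatinine") and "Stage 1 (corrected creatinine 1.5-1.99 times screening creatinine"), with further limits at 2 and 3 times screening.

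The primary analysis in SAP 5.5.1 rests on this variable: "Logistic regression of AKI (50% increase in corrected creatinine within 48 hours) with treatment group independent variable will be used for the primary outcome".

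For later times, 4.4.3 defines AKI at 96 hours in the manner of the primary endpoint, 5.5.2 plans an analysis up to 96 hours, and Figures 14.1, 14.2 and 14.4 run to 96 hours or day 4.

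**The concern.** One variable has two definitions that differ in printed unit and by a division by 1000, and the faulty version is in the primary-endpoint section. In 4.4.1 the division applies to the postoperative value only. The text does not say that the screening value is rescaled to match. A programmer following 4.4.1 alone, with laboratory values in µmol/L, would obtain a primary endpoint that no infant can reach.

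The programmer would notice and repair this, but the SAP should settle the repair in advance. Because the balance is recorded in ml and the formula needs litres, the 1000 could be taken to belong to the fluid term. That is only an inference about how a repair might go, but it is why the unit conversion should be written down.

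A smaller gap concerns day 4. Corrected creatinine stops at day 3, while some AKI outputs extend to 96 hours.

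**Working it through.** The SAP states no numerical result for this formula, so there is nothing to reproduce. The check evaluates both formulas on the same infant.

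**Inputs from the SAP.** Formulas from 4.4.1 and 4.4.3; AKI threshold 1.5 times screening; body-water fraction 0.6; preoperative creatinine in µmol/L (4.1.3), taken to be the screening value.

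**Assumed values (illustration only).** Screening creatinine 25 µmol/L, day-2 creatinine 50 µmol/L, weight 5 kg, fluid balance +0.3 L.

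**Fluid factor.** 1 + 0.3/(5 × 0.6) = 1.10.

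| Reading | Corrected value | Screening value | Ratio | Result |
|---|---|---|---|---|
| 4.4.3 | 50 × 1.10 = 55 | 25 | 2.2 | AKI, stage 2 |
| 4.4.1, µmol/L entered, only the postoperative value divided | 50/1000 × 1.10 = 0.055 | 25 | 0.0022 | no AKI |
| 4.4.1, input first converted to µmol/ml, then divided | 0.05/1000 × 1.10 = 0.000055 | 25 | 0.0000022 | no AKI |
| 4.4.1, both values divided by 1000 | 0.055 | 0.025 | 2.2 | AKI, stage 2 |

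The discrepancy against 4.4.3 is thus a factor of 1000, 10^6 or 1, depending on the reading.

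**Could any infant reach 1.5 if only the postoperative value is divided?** Let b be the fluid balance in L/kg. The rise in measured creatinine needed is 1500/(1 + b/0.6):

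- b = 0: 1,500-fold, against 1.5-fold under 4.4.3.
- b = 0.10 (an assumed extreme): 1500/1.1667 = 1,286-fold, against 1.29-fold under 4.4.3.

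At that balance even a 10-fold rise gives 10/1000 × 1.1667 = 0.0117, against 11.7 under 4.4.3. No infant would qualify. The primary definition has no dialysis criterion, so the logistic regression would have no events.

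**Does the printed unit explain the division?** Going from µmol/ml to µmol/L is a multiplication by 1000. Dividing µmol/L by 1000 does give µmol/ml, but then the comparator must be divided as well, and 4.4.1 does not say so.

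**What if the 1000 is moved to the fluid term?** With the balance in ml this is right. With the balance already in litres, as 4.4.1 prints it, the factor becomes 1 + 0.0003/3 = 1.0001 and the correction vanishes. An infant at 35 against 25 µmol/L would then score 1.40 (no AKI) instead of 35 × 1.10/25 = 1.54 (AKI).

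**Day 4.** Take the same assumed infant, below 1.5 through day 3, with factor 1.10 if a correction is made:

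- Day-4 creatinine 35: 1.40 uncorrected (no AKI), 1.54 corrected (stage 1).
- Day-4 creatinine 40: 40/25 = 1.60 uncorrected, 1.76 corrected; AKI either way, but not if day 4 is left out.

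Under the next-day rule a day-4 correction would need a day-5 balance. The follow-up variables in 4.4.3 are headed postoperative days 1-4, and the status and medication forms in 4.2.2 end at day 4. The SAP therefore does not establish that this balance exists.

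**The case against.** The strongest defence is that a relative increase does not depend on the unit. Laboratory values are in µmol/L, and dividing by 1000 gives the µmol/ml that 4.4.1 names. If the screening value is put in the same unit, the ratio is 2.2, identical to 4.4.3. On that view the defect is an unstated unit for the comparator. This stands as a possible reading, and for that reason a reader should not conclude that the two sections are irreconcilable or that a factor of 1000 is the only consequence. It does not make 4.4.1 correct: the unit is printed before the division, and nothing rescales the comparator.

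A second defence is that the slip is harmless, because zero events would be noticed and 4.4.3 gives the working form. That is fair as to its effect. It supports treating this as a simple correction, but not leaving the text as it is.

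On day 4, it can be argued that the day 1-3 limit is itself the rule, that an analysis up to 96 hours can be run on days 1-3, that stage 3 can also arise from dialysis, and that raw creatinine fills day 4 of Figure 14.4. These points largely stand. They show that the outputs can be produced, but not which rule the SAP intends. If day 4 is omitted, creatinine-based AKI up to 96 hours simply repeats the 72 h result.

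**Conclusion.** The corrected-creatinine formula in SAP 4.4.1 is wrong as written and inconsistent with 4.4.3. This is a drafting error in the primary-endpoint definition. If only the postoperative value is divided, the ratio is 1000 times too small, or 10^6 times if the input is first converted to µmol/ml; no infant meets creatinine-based AKI and the primary regression has no events. If both values are scaled, nothing changes. The factors follow from the formulas; the patient values are illustrative assumptions.

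A reader might infer that the primary analysis is unworkable or its result biased. The documents do not support that. The literal formula fails visibly, 4.4.3 supplies the intended form under the same name and rules, and nothing shows that the 4.4.1 version was ever programmed.

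The day-4 gap is a minor clarification. It touches only the complementary 96 h outputs and not the 48 h primary endpoint.

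**What to change.** In SAP 4.4.1, replace the formula with the 4.4.3 form: corrected creatinine (µmol/L) = creatinine (µmol/L) × [1 + fluid balance (L) / (weight (kg) × 0.6)], with fluid balance (L) = recorded ml/1000, compared with uncorrected screening creatinine in µmol/L. State that this one formula governs both sections. Keep the next-day balance rule and the negative-balance rule unchanged, and leave the age-differentiated version in 4.4.3 as a separate secondary variable. This is a one-line edit and needs no new data.

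Before unblinding, add one sentence reconciling the day-3 limit with AKI at 96 hours, the 96 h stage and Figure 14.4. For example, end the corrected series and corrected-creatinine AKI at 72 hours, or state which day-4 value is used. If a corrected day-4 value is wanted, the day 1-3 limit must be amended in both sections, after checking that the next-day balance was recorded.

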**Table 1 Study Activities**

	Pre-study	Surgery	Post-surgery				Follow-up		
			T0	T1	T2	T3	T4		
At:	Baseline		2 hours	6 hours	24 hours	48 hours	4, 5 days	30 days	
Informed consent	X								
Demography	X								
Weight, height	X								
Medical history	X								
Physical examination	X								
Inclusion/exclusion criteria	X	X							
Randomization		X							
Surgery		X							
Levosimendan/Milrinone		X	X	X	X	X			
Pulse, Blood pressure		X	X	X	X	X	X	X	
Routine laboratory screening (minimum Creatinine, S-K)		X	X	X	X	X	X	X	
Pharmacokinetics					X	X	X	X	
Study specific blood		X	X	X	X	X			
Continuous ECG monitoring		X	X	X	X	X	X		
Continuous hemodynamic and respiratory monitoring		X	X	X	X	X			
Serious Adverse event recording		X	X	X	X	X			
Urine production		X	X	X	X	X		X	
Adverse Events registr*		X	X	X	X	X	X	X	X
Registration of mortality									X
Registration of length of stay (bed-days)									X
Routine echocardiography (preoperative, after CPB termination, first postoperative day, and at discharge)									

\* Registration of adverse events will also be performed at day 30 (e.g. telephone contact with the parents if the patient is at home)

**Figure 2** *Study flow chart*

The infusion of Levosimendan/Milrinone will start perioperatively when the patient is on cardiopulmonary bypass. The infusion will thereafter continue in the intensive care unit (ICU) and will be terminated after 24 hours. Patients in both groups will be followed up according the normal clinical routines. Routine echocardiography will be performed at pre-defined time-points as a clinical routine (pre-operatively, after termination of CPB intra-operatively, at first postoperative day, and at discharge). Extra study specific blood samples will be taken from the included patients. Patients who develop AKI will be identified by increase in s-Creatinine >50% from baseline. The usual clinical and laboratory data will be routinely obtained and recorded in the hospital electronic records. Study-specific parameters will be registered in a CRF.

Follow-up of the patients will continue 4 days after termination of Levosimendan/Milrinone infusion. The follow-up parameters, included in case report form (CRF),

include among others treatment-needling hypotension, treatment-needling arrhythmias, s-Creatinine, s-Potassium and albumin.

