## 8. BIOLOGICAL SAMPLING PROCEDURES

### 8.1 Volume of blood

The patients usually stay in the intensive care unit for 2-4 days depending on the postoperative course. Each day during the stay at the ICU, 10-15 mL blood for routine laboratory screen will be drawn. The amount of blood may increase to 25-30 mL in case of complicated postoperative conditions (disease/operation/post operative course).

In the present study extra blood will be drawn for the analysis of study-specific biomarkers e.g. inflammatory markers and the complement system, NGAL and markers of neuronal injuries.

The total volume of extra blood that will be drawn from each subject in this study is shown in Table 5.

**Table 5** *Volume of blood to be drawn from each subject*

	Time point	mL blood
T0	Prior to CPB	2 mL
T1	At the end of CPB	2 mL
T2	2 hours after termination of CPB	2 mL
T3	6 hours after termination of CPB	2 mL
T4	24 hours after termination of CPB	2 mL
At day 5 or at discharge from hospital		2 mL
Total		12 mL

The total amount of blood taken extra from the included patients will be 10 mL in the operation day and the first postoperative day. The following table shows the proportion of the extra blood taken from an included patient compared with that amount of the blood needed for normal routine clinical use. The patient in this example has a weight of 3.5 kg and a blood volume of 90 mL/kg (total blood volume  $3.5 \times 90 = 315$  mL). It should be noted that the majority of pediatric cardiac surgery patients receive either blood products or blood (or both), and the length of stay may be considerably longer. In addition to blood drawn according to table 1, at day 5 or at the discharge from hospital 2 mL blood will be drawn for among others the analysis of Levosimendan metabolites (pharmacokinetics).

**Table 6** *Blood taken for lab screen and for study-specific analyses*

Days in PICU	Routine blood samples in uncomplicated cases mL (% of total blood vol.)	Routine blood samples in complicated cases mL (% of total blood vol.)	Blood taken for this study mL (% of total blood vol.)
Day 1 (operation day)	15 (4.8 %)	30 (9.5%)	10 (3.2%)
Day 2	15 (4.8 %)	30 (9.5%)	-
Day 3	15 (4.8 %)	30 (9.5%)	-
Total after 3 PICU days	45 (14.4 %)	90 (28.5 %)	10 (3.2%)

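### The primary AKI endpoint corrects each creatinine with one day's fluid balance labelled 24 hours later, so infants near the 50% threshold can be misclassified

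*SAP*

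**What the plan says.** SAP 4.4.1 defines the primary endpoint thus: "AKI_(48 hours) is defined as 50% increase in corrected creatinine within 48 hours". The comparison is set out as: "AKI_(48 hours) is calculated using screening creatinine (uncorrected) compared to 24 and 48 hours corrected creatinine". The corrected value is creatinine multiplied by one plus fluid balance over 0.6 times body weight. The fluid balance carries a +24 hours subscript, negative balances are set to zero, and the correction is "only calculated for day 1-3". The timing rule is spelled out: "For example for day 1 the Fluid balance measured at day 2 will be used". SAP 4.4.3 repeats the subscript and the example, both for corrected creatinine and for percentage fluid overload (%FO), so this is not an isolated slip.

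Creatinine is a morning value; 4.4.3 lists it under "Morning lab results (Postop day 1 is under hemodynamics_1, etc". The same section has a cumulative fluid measure, but only for fluid overload: "Cumulative %FO (day 1+2, day 1+2+3, day 1+2+3+4".

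The protocol uses no fluid correction. Under Figure 2 in section 3 it says: "Patients who develop AKI will be identified by increase in s-Creatinine >50% from baseline". In SAP 5.5.1 the corrected AKI status is the dependent variable of the primary logistic regression.

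**The concern.** A fluid correction is meant to undo the dilution present when the blood is drawn. Only fluid retained up to that moment can have diluted the sample, and all of it counts, not one day's share. A balance that accrues over the 24 hours after the sample does neither job. An infant overloaded during the first night who then diureses gets a correction factor of exactly 1, because the negative balance is floored at zero. An infant not diluted at sampling who is given fluid afterwards has the creatinine inflated.

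This rule decides who counts as an event in the primary analysis. Errors in a binary outcome blur the comparison between arms. They could also carry a non-renal signal: protocol 7.1.15 treats hypotension first with fluid, and 7.1.4 lists hypotension as a reaction to both drugs. Post-sample fluid may therefore reflect haemodynamics rather than kidney function.

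**Working it through.** **Inputs from the SAP.** Threshold ratio 1.5 (4.4.1; stage 1 in 4.4.3 also starts there); body-water fraction 0.6; negative balances set to zero; samples at 24 and 48 hours. I use the formula as printed in 4.4.3, in µmol/L. The 4.4.1 version prints a different unit and a division by 1000.

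Factor = 1 + max(balance in L, 0) / (0.6 × weight in kg). AKI if factor × (creatinine / screening creatinine) ≥ 1.5.

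**Which infants can be affected.** The uncorrected ratio needed to reach 1.5 is 1.5 / factor:

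| Balance entered (mL/kg) | Factor | Ratio needed |
|---|---|---|
| 0 or negative | 1.000 | 1.500 |
| +20 | 1.033 | 1.452 |
| +40 | 1.067 | 1.406 |
| +60 | 1.100 | 1.364 |
| +80 | 1.133 | 1.324 |
| +100 | 1.167 | 1.286 |

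Over this range, the choice of balance matters only for uncorrected ratios of about 1.29 to 1.50.

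**Worked cases.** Patient values are assumed: weight 6 kg, so the denominator is 0.6 × 6 = 3.6 L. Cases 1 and 2 take a screening creatinine of 25 µmol/L and show the day-1 value alone.

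1. Day-1 creatinine 33, +500 mL before the sample, negative balance afterwards. SAP read literally: 33/25 × 1 = 1.32, no AKI. Balance up to the sample: 1.32 × (1 + 0.5/3.6) = 1.503, AKI.
2. Day-1 creatinine 35, no gain before the sample, +300 mL afterwards. SAP read literally: 35/25 × (1 + 0.3/3.6) = 1.517, AKI. Balance up to the sample: 1.40, no AKI.
3. 48-hour sample, uncorrected ratio 1.35, successive daily balances +0.30, +0.12 and −0.06 L, the first two closing before the sample. SAP read literally (third balance, floored): 1.35. One-day balance closing at the sample: 1.35 × (1 + 0.12/3.6) = 1.395. Cumulative: 1.35 × (1 + 0.42/3.6) = 1.508. Only the cumulative rule reaches AKI, so correcting the timing alone does not settle the 48-hour value.

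**Simulation.** The documents give no fluid balances, creatinine spread or AKI rate, so every input is an assumption:

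- uncorrected ratio lognormal, median 1.1 to 1.3, log-SD 0.2 or 0.3, correlation 0.7 between the two days;
- mean daily balances of (30, 0, −10), (50, 10, −20), (80, 20, −20) or (20, 20, 20) mL/kg;
- SD 20 or 40 mL/kg, with day-to-day correlation 0 or 0.5.

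The literal SAP rule was compared with the cumulative balance up to each sample. AKI status differed in about 2.5 to 16 of 70 infants. AKI was missed in about 3 to 23% of infants and added in 0 to 4%. With median 1.2, log-SD 0.3 and balances of +50/+10/−20 mL/kg, AKI was 34% under the SAP rule and 44% under the cumulative rule. With a steady +20 mL/kg per day it was 37% against 39%.

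**What the label might mean.** The SAP does not state the clock window of a balance measured at day 2, and its own labels conflict:

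- Section 4.2.2 makes the first status page the operative day and the second page postoperative day 1. For dialysis, 4.4.3 calls those same two pages day 1 and day 2.
- Morning laboratory values for postoperative day 1 sit on the first page of their own series.
- Fluid overload uses the same +24 hours rule but is cumulated to day 4. Literally that needs a day-5 balance, although the section covers days 1 to 4.
- Limiting corrected creatinine to days 1 to 3 fits a genuine one-day lead, but Figure 14.4 in SAP 8.2 plots it to day 4.

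**The case against.** The best counter-argument is that the timing fault is not proven. If fluid balance is recorded on the status pages, which the SAP does not say, then moving from day 1 to day 2 may only align two page series numbered one apart. If the balance so chosen closes by the time of the morning sample, the first-day timing fault disappears. This stands: a reader might infer that the diluting fluid is certainly left out, and the documents do not establish that. It does not rescue the rule. The +24 hours label would then mislead, two programmers could give the same infant different AKI status, and the 48-hour value would still rest on one day's balance.

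Three further inferences are tempting and unsupported:

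- **Missing day-3 balances.** Protocol 8.1 says "The patients usually stay in the intensive care unit for 2-4 days depending on the postoperative course", which might suggest that infants who recover quickly lack the balance needed at 48 hours. But protocol section 3 continues follow-up on the ward, SAP 1.2 follows patients for at least 48 hours after treatment ends, and SAP 4.4.3 lists fluid balance for postoperative days 1 to 4. The value is planned.
- **Bias between arms.** Fluid treatment of hypotension gives a route to it. Nothing in the documents shows that post-sample fluid will differ by arm, and the study-drug infusion is blinded and equal in rate and volume.
- **A definite count of misclassified infants.** A change needs a ratio near the threshold and a sizeable difference in balance. Case 1 needs at least (1.5/1.32 − 1) × 3.6 = 0.491 L, about 82 mL/kg, followed by a non-positive day. Final status also depends on the other day's value.

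Uncorrected creatinine is reported and plotted beside the corrected value, which gives some transparency. The SAP does not, however, name an analysis of AKI status based on it.

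**Conclusion.** The concern holds in conditional form. As written, the primary endpoint uses a single day's balance labelled 24 hours after the creatinine sample. On the literal reading this is the wrong fluid. On the page-index reading the label is misleading and the 48-hour correction is still incomplete. Infants with uncorrected ratios of roughly 1.3 to 1.5 can be misclassified in either direction; when early overload is followed by diuresis, the error is mainly missed AKI.

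The range of about 2.5 to 16 of 70 rests on assumed inputs, on the literal reading, and on taking the cumulative pre-sample balance as the reference. It shows that the effect need not be trivial; it is not an estimate for this trial. Because the rule determines the primary outcome, and the SAP gives no reason for the lead, it should be settled before unblinding.

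**What to change.** In SAP 4.4.1 and 4.4.3, before unblinding:

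1. State the start and end time of each recorded fluid balance, and reconcile the day numbers with the CRF page numbers in 4.2.2 and 4.4.3.
2. Correct each creatinine with the cumulative net balance from the earliest recorded postoperative balance (PICU arrival if intraoperative volumes are not quantified) up to that sample. Delete the +24 hours rule.
3. If a floor at zero is kept, apply it to the cumulative sum only.
4. Add a supportive analysis of AKI by uncorrected creatinine, more than 50% above baseline, as in protocol section 3.
5. Record the change in SAP section 7, which at present holds only a template instruction.

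The cost is mainly wording and programming, since daily balances are already among the SAP variables. Whether a balance closing at the first morning sample can be recovered depends on the CRF and must be checked first. AKI counts will change. Intraoperative fluid may not be recoverable, because SAP 4.2.1 records the listed blood products and albumin as yes/no and only diuresis in mL.
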